### 7.3.5 Interim analyses

#### **Single rising dose parts under fasting and fed conditions**

##### Preliminary safety analysis

No formal interim safety analysis is planned. However, if safety reasons require a preliminary safety analysis of ECG data, a part of the staff of the ECG laboratory may be unblinded. This part of the staff is strictly separated from the other part of the staff, which is involved with interval measurements and assessments of single ECGs (they keep blinded).

##### Preliminary PK analyses

A preliminary analysis of PK parameters ( $C_{\max}$  and  $AUC_{0-24}$  of BI 705564) provided as individual values and gMeans at least of the first cohort per dose level, will be performed for each dose group before proceeding to the next higher level. Data from the first cohorts of the above mentioned dose levels will be sufficient as long as the data from at least 2 subjects on active are available.

In contrast to the final PK calculations, the preliminary analysis will be based on planned sampling times rather than on actual times, regardless of whether actual times were within the time windows or not. Therefore, minor deviations of preliminary and final results may occur.

The preliminary results will be distributed to the investigator and the trial team.

Depending on the results of available preliminary PK analyses, the tolerability and safety of the compound, and changes of dosing schedule (e.g. additional intermediate doses), additional PK preliminary analysis may be performed based on the request of the Trial Clinical Monitor, the investigator, or Trial Clinical Pharmacokineticist. No formal preliminary PK/PD report will be written.

No inferential statistical interim analysis is planned. However, after each dose group the investigator (or deputy) is allowed to postpone further dose progression until a preliminary analysis of the data already obtained has been performed.

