##### Single rising dose part under fasting conditions

This part is designed single-blind, partially randomised, and placebo-controlled within parallel dose groups.

A total of 48 healthy male subjects is planned to participate in the single rising dose part under fasting conditions, resulting in 6 sequential groups comprising 8 subjects each.

Within each dose group, 6 subjects will receive the active drug and 2 will receive placebo. Only one dose is tested within each dose group. Dose groups will be treated consecutively in ascending order of doses. Each dose group will consist of 2 cohorts of 4 subjects each (3 on active drug and 1 on placebo).

On the first study day within each dose group, the first cohort will be treated in a single-blind manner in the following order: First subject (active) followed at least 1 hour later by the second subject (placebo) followed at least 1 hour later by the third subject (active) followed at least 10 minutes later by the fourth subject (active).

If BI 705564 treatment is safe and showed acceptable tolerability in the first cohort, subjects in the second cohort will be treated not earlier than 2 days later (at least 46 h between the 1st subject of each cohort) in a single-blind, randomised manner. In the second cohort, a time interval of at least 10 minutes will be maintained between administrations of trial drug to the individual subjects.

A time interval of at least 10 days will be maintained between the first drug administration in the previous dose group and the first drug administration of the subsequent dose group. The dose groups to be evaluated are outlined in Table 3.1: 1 below.

Table 3.1: 1 Dose groups in the single rising dose part under fasting conditions

Dose Group	1	2	3	4	5	6
Dose (mg) q.d.	1	3	10	20	40	80
Formulation	PfOS	PfOS	Tab	Tab	Tab	Tab
Number of subjects	8	8	8	8	8	8
Subjects with placebo	2	2	2	2	2	2
Subjects with active drug	6	6	6	6	6	6

The decision to proceed to the next dose group will be based upon the safety, tolerability and pharmacokinetic data of the preceding dose groups. The next dose will only be given, if, in the opinion of the investigator, no safety concerns arose in the preceding dose group (i.e. no dose-limiting events occurred) and, if none of the pre-specified trial-specific stopping criteria were met (see [Section 3.3.4.2](#)).

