\* For technical reasons related to drug packaging, numbers 9-11 cannot be attributed to dose groups in the SRD part under fed conditions.

The decision to proceed to the next dose group will be based upon the safety, tolerability and pharmacokinetic data of the preceding dose groups. The next dose will only be given, if, in the opinion of the investigator, no safety concerns arose in the preceding dose group (i.e. no dose-limiting events occurred) and, if none of the pre-specified trial-specific stopping criteria were met (see [Section 3.3.4.2](#)).

A documented Safety Review must take place prior to each dose escalation. Furthermore, an unscheduled safety review meeting can be requested at any time for any reasonable cause by the Principal Investigator (or an authorised deputy) or the sponsor of the study, e.g. because of any unforeseen adverse events, etc. Dose escalation will only be permitted, if no safety concerns exist in the opinion of the Principal Investigator (or an authorised deputy) and the Trial Clinical Monitor (or an authorised deputy).

The minimum data set for review consists of the following data:

- AEs in the current and preceding dose groups up to at least 48 h post dosing, including clinically relevant findings from ancillary safety testing, as listed below.

Note: AEs may be ongoing at the time of Safety Reviews and AE information may be subject to change prior to Database Lock.

- Results from 12-lead ECG and continuous ECG monitoring in the current and preceding dose groups up to at least 48 h post dosing.
- Vital signs in the current and preceding dose groups up to at least 48 h post dosing.
- Clinical laboratory tests in the preceding dose groups and clinical laboratory tests of the first cohort of the current dose group up to at least Visit 2 Day 8.
- Preliminary PK data for selected time points, as per [Section 7.3.5](#).
- Check of criteria for stopping subject treatment, as per [Section 3.3.4.1](#).

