#### 3.3.4.2 Discontinuation of the trial by the sponsor

BI reserves the right to discontinue the trial overall or at a particular trial site at any time for any of the following reasons:

1. New toxicological findings or serious adverse events invalidate the earlier positive benefit-risk-assessment. More specifically, the trial will be terminated, if more than 50% of subjects show drug-related and clinically relevant adverse events of moderate or severe intensity or, if at least one drug-related serious adverse event is reported that is considered to be unacceptable.
2. The expected enrolment goals overall or at a particular trial site are not met.
3. Violation of GCP, or the CTP by a trial site or investigator, disturbing the appropriate conduct of the trial.
4. The sponsor decides to discontinue the further development of the investigational product.
5. Dose escalation will be stopped as soon as at least 2 subjects at one dose level on active drug shows relevant individual QT prolongation, i.e. a QTc increase of greater than 60 ms from baseline in connection with absolute QT or QTc greater than 500 ms which has been confirmed by a repeat ECG recording.
6. Dose escalation will be stopped, if the  $C_{max}$  or  $AUC_{0-24}$  of at least 2 subjects of one dose group increases above the following exposure thresholds or, if the estimated gMean exposure of the next dose group is expected  
Estimation will be done based on preliminary pharmacokinetics results of preceding dose groups (see [Section 7.3.5](#)).

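### The individual-exposure stopping rule is counted over a whole dose group, but escalation may go ahead on first-cohort PK alone, so a group that meets the rule can be passed

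*Protocol*

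**What the plan says.** Four provisions of the protocol bear on this.

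- **The rule.** Section 3.3.4.2, item 6, has two limbs. Under the first, escalation stops if Cmax or AUC0-24 "of at least 2 subjects of one dose group increases above the following exposure thresholds". Under the second, it stops when the gMean projected for the following group would pass a limit. The limits themselves are not visible in the public text. For the second limb, "Estimation will be done based on preliminary pharmacokinetics results of preceding dose groups", with a pointer to Section 7.3.5.
- **The unit.** Section 3.1, in the same terms for both single rising dose parts: "Within each dose group, 6 subjects will receive the active drug and 2 will receive placebo". The split into cohorts is also given there: "Each dose group will consist of 2 cohorts of 4 subjects each (3 on active drug and 1 on placebo").
- **The gate.** Section 3.1 allows the next dose only "if none of the pre-specified trial-specific stopping criteria were met", citing Section 3.3.4.2.
- **The data.** The Safety Review minimum data set in Section 3.1 lists "Preliminary PK data for selected time points, as per" Section 7.3.5. That section asks for individual values and gMeans from the first cohort as a minimum, and says that first-cohort data "will be sufficient as long as the data from at least 2 subjects on active are available".

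The check of stopping criteria listed in the same data set cites Section 3.3.4.1 (removal of individual subjects), not Section 3.3.4.2. The visible SAP text does not deal with escalation.

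**The concern.** The rule and the data it is checked on have different denominators. Item 6 asks for 2 exceedances among 6 actives. On the permitted minimum it can be recognised only if 2 of 3, or 2 of 2, exceed. The second-cohort results that would complete the count need not be available when the decision is taken. The protocol does not say what follows if they complete it after the next dose has been given.

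This is an exposure barrier in a first-in-human escalation. On the minimum data set, its individual limb is less sensitive than its wording suggests. The escalation at issue is the fed part. The rationale for global amendment 4 records the fasting part as completed. The fed part escalates by factors of 2 (Section 2.3.2.7), from 20 to 160 mg, and was added after food-effect data suggested that food may raise bioavailability (Section 3).

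**Working it through.** The plan states no operating characteristic for this rule, so there is no figure to reproduce.

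**Inputs**
- Actives per dose group: 6; per cohort: 3 (Section 3.1).
- Individual limb: at least 2 subjects of the group above the threshold (Section 3.3.4.2, item 6).
- Actives with PK at the decision: m = 3 (first cohort) or m = 2 (lowest number accepted in Section 7.3.5).
- Assumption: the actives seen are a random draw from the 6, that is, actives are exchangeable between cohorts.

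**1. Miss rate given the number of exceeders**

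Let K of the 6 actives exceed. The individual limb is visible if at least 2 of the K are among the m seen (hypergeometric).

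For m = 3: P(seen) = [C(K,2)·C(6−K,1) + C(K,3)] / C(6,3), with C(6,3) = 20.
- K = 2: (1·4 + 0)/20 = 4/20
- K = 3: (3·3 + 1)/20 = 10/20
- K = 4: (6·2 + 4)/20 = 16/20
- K = 5: (10·1 + 10)/20 = 20/20

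For m = 2 both must exceed: P(seen) = C(K,2)/C(6,2), with C(6,2) = 15. This gives 1/15, 3/15, 6/15 and 10/15 for K = 2 to 5.

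| Exceeders among 6 | Missed, 3 seen | Missed, 2 seen |
|---|---|---|
| 2 | 80% | 93.3% |
| 3 | 50% | 80% |
| 4 | 20% | 60% |
| 5 | 0% | 33.3% |
| 6 | 0% | 0% |

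With all 6 seen, nothing is missed for any K.

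**2. Averaged over the number of exceeders**

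If each active exceeds independently with probability p, then P(missed | group meets the rule) = 1 − P(at least 2 of m)/P(at least 2 of 6).
- p = 0.1, m = 3: 1 − 0.0280/0.1143 = 75.5%
- p = 0.3, m = 3: 1 − 0.2160/0.5798 = 62.8%
- p = 0.5, m = 3: 1 − 0.5000/0.8906 = 43.9%
- m = 2 at the same p: 91%, 84.5% and 71.9%

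With 3 actives seen, a miss is more likely than not only while p is below about 0.44.

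**3. The projected-gMean limb**

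Its limits are not shown, so only an assumption-based range is possible. The simulation took lognormal exposure, a dose-proportional doubling, an individual threshold of 1 to 3 times the gMean limit, and p from 0.1 to 0.5, with 400,000 groups per case. Among groups that meet the individual limb, the share missed by both limbs was:

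| gCV | 3 seen | 2 seen |
|---|---|---|
| 30% | 0–0.7% | 0–3% |
| 50% | 0–13% | 0–19% |
| 80% | 0–35% | 0–38% |

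The highest values arise when the individual threshold equals the gMean limit and p = 0.1.

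**The case against.** The strongest reply is that Section 7.3.5 sets a floor and that other safeguards surround it.

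- *More PK can be used.* The monitor, the investigator or the pharmacokineticist may request further preliminary PK analyses, and the investigator may postpone progression. Nor does the timetable prevent fuller data. At the earliest permitted dosing, second-cohort 24 h samples are drawn by 46 + 0.5 + 24 = 70.5 h, against 240 h for the earliest next group. All of this stands. But the discretion is optional while item 6 is mandatory, no maximum interval between cohorts is set, and no bioanalytical turnaround is given.
- *The gMean limb catches it.* Often it would, as step 3 shows, and Section 2.3.2.7 makes the projected gMean a condition of each step (except Dose Group 1 to 2, fasting). But it rests on the same 2 or 3 subjects. It protects less if exposure rises less than proportionally, which Section 3 suggests for high fasting doses. The individual limb was also written as a separate ground for stopping.
- *First-cohort minima are deliberate.* The Safety Review list uses one for laboratory data too. That explains the choice for PK but does not align it with a rule counted over the group.

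A reader might infer that a group meeting the rule will usually be passed unseen. The documents do not support that. It would require escalation on the bare minimum, a criterion only just met, and a gMean limb that also fails. The 2-active figures further require that one first-cohort active has no data. With 3 seen, the miss falls to 50% at 3 of 6 and 20% at 4 of 6.

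**Conclusion.** The inconsistency is real. Item 6 is counted over 6 actives, and nothing visible in the protocol requires PK from more than the first cohort, or from more than 2 actives, before the next dose. Escalation on that minimum can pass a group that meets the individual limb. The miss is largest when the rule is only just met and disappears at 5 of 6 with 3 seen, or at 6 of 6 with 2 seen.

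The exact figures rest on exchangeability between cohorts. They are miss rates of one limb, not the chance that escalation proceeds. That chance cannot be fixed, because the limits, the variability and the probability of exceedance are not available. The point applies to the fed steps 20 to 40, 40 to 80 and 80 to 160 mg, and to any doses added there; the top dose has no next level. It should be settled before item 6 is relied on for those steps.

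**What to change.** Reconcile Section 3.3.4.2 (item 6), the Safety Review minimum data set in Section 3.1 and Section 7.3.5, so that the subjects over whom item 6 is counted are the same subjects whose Cmax and AUC0-24 must be available when it is checked before escalation. State also what follows if second-cohort PK that arrives later meets the criterion after the next dose has been given. In the same edit, check whether the Safety Review list should refer to Section 3.3.4.2 as well as Section 3.3.4.1.

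Which passage changes is for the sponsor, and no clinical rule is proposed here. The cost is protocol wording and, depending on how it is resolved, possibly earlier PK availability or a short wait before the next group.

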#### **Food effect part**

##### Preliminary PK analyses

A preliminary analysis of PK parameters ( $C_{\max}$  and  $AUC_{0-24}$  of BI 705564), provided as individual values and gMeans, will be performed before proceeding to the next higher level. Data from at least 6 subjects are needed to be available before proceeding to the next higher level.

In contrast to the final PK calculations, the preliminary analysis will be based on planned sampling times rather than on actual times, regardless of whether actual times were within the time windows or not. Therefore, minor deviations of preliminary and final results may occur.

The preliminary results will be distributed to the investigator and the trial team.

No formal preliminary PK/PD report will be written.

**Note:** Due to global amendment No 4, only one dose level (10 mg) is given in the food effect part. Therefore, proceeding to the next higher level in the food effect part is not applicable.

### 7.3.6 Pharmacokinetic analyses

The pharmacokinetic parameters listed in [Section 5.5.1](#) for drug BI 705564 will be calculated according to the BI SOP 'Standards and processes for analyses performed within Clinical Pharmacokinetics/Pharmacodynamics' [[001-MCS-36-472](#)].

Subjects who are not included in the PKS (see [Section 7.3.1](#)) will be reported with their individual plasma (single rising dose parts under fasting and fed conditions, and food effect part) and urine (single rising dose parts, only) concentrations and individual pharmacokinetic parameters; however, they will not be included in descriptive statistics for plasma (single rising dose parts under fasting and fed conditions and food effect part) and urine (single rising dose parts, only) concentrations or pharmacokinetic parameters.

Only concentration values within the validated concentration range and actual sampling times will be used for the calculation of pharmacokinetic parameters. Concentrations used in the pharmacokinetic calculations will be in the same format provided in the bioanalytical report, (i.e., to the same number of decimal places provided in the bioanalytical report).

If a pre-dose concentration value is greater than 5% of  $C_{max}$ , the subject's pharmacokinetic data will be not included in any statistical evaluations, in accordance with international guidance. The individual pharmacokinetic parameters of such a subject will be calculated and listed separately. If a pre-dose concentration is above BLQ, but less than or equal to 5% of the subject's  $C_{max}$  value, the subject's data without any adjustments will be included in all pharmacokinetic measurements and calculations.

## 7.4 HANDLING OF MISSING DATA

### 7.4.1 Safety

With respect to safety evaluations, it is not planned to impute missing values.

### 7.4.2 Plasma/urine drug concentration - time profiles

Handling of missing PK data will be performed according to the relevant SOP of the Sponsor [[001-MCS-36-472](#)].

Drug concentration data identified with NOS (no sample available), NOR (no valid result), NOA (not analysed), BLQ (below the lower limit of quantification), or NOP (no peak detectable) will be displayed as such and not replaced by zero at any time point (this rule also applies also to the lag phase, including the pre-dose values).

### 7.4.3 Pharmacokinetic parameters

Handling of missing PK data will be performed according to the relevant SOP of the Sponsor [[001-MCS-36-472](#)].

For the non-compartmental analysis, concentration data identified with NOS, NOR or NOA will generally not be considered. Concentration values in the lag phase identified as BLQ or NOP will be set to zero. All other BLQ/NOP values of the profile will be ignored. The lag phase is defined as the period between time zero and the first time point with a concentration above the quantification limit.

## 7.5 RANDOMISATION

### Single rising dose parts under fasting and fed conditions

Each dose group will be divided into two cohorts. The subjects of the first cohort will not be randomised to maintain a treatment sequence of active-placebo-active-active due to safety reasons. In the second cohort of each dose level the subjects will be assigned to active or placebo treatment using a 3:1 allocation ratio.

The Sponsor will arrange for the randomisation as well as packaging and labelling of trial medication. The randomisation list will be generated using a validated system, which involves a pseudo-random number generator and a supplied seed number so that the resulting allocation is both reproducible and non-predictable.

The randomisation list will contain additional blocks to allow for subject replacement (see [Section 3.3.5](#)).

### **Food effect part**

Subjects will be randomised to one of the two treatment sequences in a 1:1 ratio. The block size will be documented in the CTR.

The sponsor will arrange for the randomisation as well as packaging and labelling of trial medication. The randomisation list will be generated using a validated system, which involves a pseudo-random number generator and a supplied seed number so that the resulting allocation is both reproducible and non-predictable.

The randomisation list will contain additional blocks to allow for subject replacement (see [Section 3.3.5](#)).

## **7.6 DETERMINATION OF SAMPLE SIZE**

### **Single rising dose part under fasting conditions**

It is planned to include a total of 48 subjects in this part of the trial. The planned sample size is not based on a power calculation. The size of 8 subjects per dose group (6 on active treatment, and 2 on placebo) is commonly used in single-rising dose studies of the present type and is in general considered as sufficient for the exploratory evaluation of single dose safety and pharmacokinetics [[R95-0013](#)].

### **Single rising dose part under fed conditions**

It is planned to include a total of 32 subjects in this part of the trial. The planned sample size is not based on a power calculation. The size of 8 subjects per dose group (6 on active treatment, and 2 on placebo) is commonly used in single-rising dose studies of the present type and is in general considered as sufficient for the exploratory evaluation of single dose safety and pharmacokinetics [[R95-0013](#)].

### **Food effect**

It is planned to enter a total of 12 subjects in this part of the trial. The planned sample size is not based on a power calculation but is judged to be adequate to attain reliable results and to fulfil the objectives and requirements of this exploratory trial.

With a sample size of 12 subjects, the following precision of the ratio of gMeans (test/reference) can be expected. Precision is defined as the ratio of upper to lower confidence interval limit. Note that the precision is independent of the actual ratio of gMeans.

For this trial, no information on intra-subject variability is available from previous trials. Therefore, [Table 7.6: 1](#) provides an overview on the achievable precision for estimating the ratio of gMeans (test/reference) for three different gCV. For illustrative purposes, the expected 90% confidence intervals with 95% coverage probability are displayed for different values of gMeans ratios T/R in the two-period two-sequence crossover design.

Table 7.6: 1 Precision that can be expected with 95% tolerance probability and illustrative two-sided 90% confidence intervals around the ratios of gMeans (T/R) for different gCVs in a 2x2 crossover trial in one dose group (N=12).

gCV [%]	Precision upper CL / relative BA estimate	Ratio [%]*	Lower CL [%]	Upper CL [%]
20	1.22	80	65.61	97.54
20	1.22	100	82.01	121.93
20	1.22	125	102.52	152.41
20	1.22	150	123.02	182.89
20	1.22	200	164.03	243.86
25	1.28	80	62.52	102.36
25	1.28	100	78.15	127.95
25	1.28	125	97.69	159.94
25	1.28	150	117.23	191.93
25	1.28	200	156.31	255.91
30	1.34	80	59.63	107.33
30	1.34	100	74.54	134.16
30	1.34	125	93.17	167.71
30	1.34	150	111.80	201.25
30	1.34	200	149.07	268.33

\*Ratio of gMeans (test/reference) for a PK endpoint is defined by  $\exp(\mu_T)/\exp(\mu_R)$ .

The calculation was performed as described by Julious [R11-5230] using R Version 3.2.2.

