### **Food effect part**

The food effect of the BI 705564 tablet will be estimated by the ratios of the gMeans (test/reference) for the primary and secondary PK endpoints. Additionally, their two-sided 90% confidence intervals (CIs) will be provided. This method corresponds to the two one-sided t-tests procedure, each at the 5% significance level. Since the main focus is on estimation and not testing, an acceptance range was not specified, that is, no hypothesis will be tested.

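### Does the definition of precision in Protocol 7.6 undermine the food-effect precision table for N = 12?

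*Protocol*

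**What the plan says.** Protocol 7.6 plans 12 subjects for the food-effect part ("It is planned to enter a total of 12 subjects in this part of the trial"). It says that this number does not come from a power calculation, and then shows what precision 12 subjects can be expected to give. The text states: "Precision is defined as the ratio of upper to lower confidence interval limit". It adds that precision does not depend on the true ratio of geometric means.

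Table 7.6: 1 then lists precision of 1.22, 1.28 and 1.34 for intra-subject gCVs of 20, 25 and 30%, under the header "Precision upper CL / relative BA estimate". Beside each value it prints the lower and upper limits for five ratios (80, 100, 125, 150 and 200%), which makes 15 rows. The title reads "Precision that can be expected with 95% tolerance probability and illustrative two-sided 90% confidence intervals", while the text above says "the expected 90% confidence intervals with 95% coverage probability are displayed".

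Protocol 7.2 gives the purpose of the part: "Since the main focus is on estimation and not testing, an acceptance range was not specified".

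**The concern.** The text and the column header define the same word in two ways. With no power calculation and no acceptance range, this precision is the only quantitative statement of what 12 subjects can deliver, so its definition ought to match the figures shown.

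A reader who took the sentence literally and applied it to 1.22 would infer limits of about 90.5% to 110.5% around a ratio of 100%. The table prints 82.01% to 121.93%. The error would run one way only: the interval would look half as wide on the log scale as it is. If the sentence were right and the column wrong, the achievable precision would have been overstated at the design stage.

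The two names for the 95% probability (coverage in the text, tolerance in the title) add to the impression of a loosely specified calculation.

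**Working it through.** **Inputs.** All are from Protocol 7.6: N = 12; a 2x2 crossover, so N - 2 = 10 residual degrees of freedom; a two-sided 90% interval, so the 0.95 quantile of t; 95% tolerance probability; gCV 20, 25 and 30%.

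**Step 1: reproduce the printed figures.** The log-scale within-subject standard deviation is σ = sqrt(ln(1 + gCV²)). The half-width that the interval stays within with 95% probability is

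h = t(0.95; 10) × σ × sqrt(2/12) × sqrt(χ²(0.95; 10)/10).

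The quantiles are t = 1.8125 and χ² = 18.307. The multiplier of σ is therefore 1.8125 × 0.40825 × 1.35304 = 1.0012.

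| gCV | σ | h | exp(h) = upper / estimate | exp(2h) = upper / lower | Printed |
|---|---|---|---|---|---|
| 20% | 0.1980 | 0.1983 | 1.219 | 1.487 | 1.22 |
| 25% | 0.2462 | 0.2465 | 1.280 | 1.637 | 1.28 |
| 30% | 0.2936 | 0.2939 | 1.342 | 1.800 | 1.34 |

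The printed column is exp(h), as its header says. Multiplying and dividing each of the five ratios by exp(h) gives all 30 printed limits to two decimals.

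**Step 2: check from the printed limits alone, with no model.** At ratio 100%:

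- gCV 20%: 121.93/100 = 1.219; 121.93/82.01 = 1.487.
- gCV 25%: 127.95/100 = 1.280; 127.95/78.15 = 1.637.
- gCV 30%: 134.16/100 = 1.342; 134.16/74.54 = 1.800.

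The other 12 rows give the same ratios up to rounding. No row fits the sentence in the text.

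**Step 3: what the sentence would imply.** If a printed value P were upper/lower, the limits at ratio 100% would be 100/sqrt(P) and 100 × sqrt(P):

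- P = 1.22: 90.5 to 110.5 (printed 82.01 to 121.93).
- P = 1.28: 88.4 to 113.1 (printed 78.15 to 127.95).
- P = 1.34: 86.4 to 115.8 (printed 74.54 to 134.16).

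None of these narrower limits appears in the protocol. The limits printed in the same row contradict them.

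**Step 4: does the 95% wording matter?** Without the tolerance factor, exp(h) would be 1.16, 1.20 and 1.24, which do not match the table. The 95% was therefore applied as a tolerance probability on the estimated variance, as the title says. The word used in the text changes no figure.

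**Step 5: does anything use the definition?** Protocol 7.6 sets no precision threshold. Protocol 7.1.3 and 7.3.1 and SAP 7.4 specify a log-scale ANOVA with a 90% interval from the t-distribution; none of them refers to precision in this sense. The SAP does not restate the definition.

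**The case for a change.** The strongest argument for a correction is that the contradiction is certain and visible on one page, and would cost one sentence to remove. Expected precision is the sole quantitative support for N = 12. The remark that precision does not depend on the true ratio holds under either definition, so it does not tell the reader which is meant. Someone who later compared an achieved upper/lower ratio with the planned precision would be comparing unlike quantities.

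The factual part of this stands: the sentence does not describe the column. The consequence does not. To be misled, a reader has to pass over the header that defines the column and the two columns of limits next to it. A later comparison has no planned criterion to meet or miss. Section 3 of the protocol also records that 10 mg food-effect data were already informing design decisions when Amendment 4 was written, so the table no longer steers a decision about this part.

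**Conclusion.** This is a clerical slip with no consequence. One sentence in Protocol 7.6 names upper/lower where the table correctly shows upper/estimate. The gap between the two definitions is 1.22, 1.28 and 1.34 against 1.49, 1.64 and 1.80. It is a gap in labelling only: the precision column, all 15 pairs of limits, N = 12 and the planned 90% interval are unaffected. The difference between coverage and tolerance is likewise one of wording.

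The conclusion rests on two things. The limits reproduce from the protocol's own inputs by the standard calculation for a 2x2 crossover, and nothing in the protocol or SAP sets a criterion on precision. If a target had been stated as an upper/lower ratio, the wording would matter; none is. A sponsor revising the section for other reasons could tidy the sentence, but the plan does not need to change on this account.
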